8.4.1. SIDIAP (ES) (7 million Active Individuals)

The Information System for Research in Primary Care (Sistema d'Informació per al Desenvolupament de la Investigació en Atenció Primària' [SIDIAP]; www.sidiap.org) was created in 2010 by the Catalan Health Institute and the IDIAP JGol Institute. It includes information collected since 01 January 2006 during routine visits at 278 primary care centres pertaining to the Catalan Health Institute in Catalonia (North-East Spain) with 3,414 participating GPs. SIDIAP has pseudo-anonymised records for 7 million people (80% of the Catalan population) and is highly representative of the Catalan population. The SIDIAP data comprise the clinical and referral events registered by primary care health professionals (e.g., GPs, paediatricians, and nurses) and administrative staff in electronic medical records, comprehensive demographic information, community pharmacy invoicing data, specialist referrals, and primary care laboratory test results. The SIDIAP data can also be linked to other data sources, such as the hospital discharge database, on a project-by-project basis. Health professionals gather this information using ICD-10-CM codes, ATC codes, and structured forms designed for the collection of variables relevant to primary care clinical management, such as country of origin, sex, age, height, weight, body mass index, tobacco and alcohol use, blood pressure measurements, and blood and urine test results. Regarding vaccinations, SIDIAP includes all routine childhood and adult immunisations, including the antigen and the number of administered doses. Encoding personal and clinic identifiers ensures the confidentiality of the information in the SIDIAP database. Currently, with the COVID-19 pandemic, there is the possibility to have shorter-term updates in order to monitor the evolution of the pandemic. Recent reports have shown the SIDIAP data to be useful for epidemiological research. SIDIAP is listed under the ENCePP resources database.

8.4.2. VID ES (5 million Active Population)

The region of Valencia, with 5 million inhabitants, is part of the Spanish National Health System, a universal public healthcare system. Information will be obtained from the population-based electronic data banks of the Valencia Health Service and the regional Government of Valencia: (1) The Population Information System (SIP) provides an identification number for each individual under Valencian Health Service coverage and registers some demographic characteristics, and dates and causes of Valencia Health Service discharge, including death. (2) The minimum basic dataset at hospital discharge is a synopsis of clinical and administrative information on all hospital discharges, including diagnoses and procedures (all electronic health systems in the Valencian Health Service use the ICD- 9-CM and ICD-10-CM). (3) The Emergency Department module including emergency department dates of visit and discharge and reason for discharge. (4) The electronic medical record (EMR) for ambulatory care, is available in all primary healthcare centres and other ambulatory settings. It has all the information on patients regarding diagnoses, their personal and family medical history, laboratory results, lifestyle, etc (5) The pharmaceutical module (prescription information system), part of EMR, includes information about both physician prescriptions and dispensations from pharmacy claims. (6) The Corporate Resource Catalogue provides information about the geographical and functional organisation of Valencian Health Service, its health centres, health services provided and professionals in healthcare. Specific public health registries are available and linkable at an individual level (such as the perinatal registry and the congenital anomalies registry, from which pregnancy outcomes

can be obtained) All the information in these systems can be linked at an individual level through the SIP number.

8.4.3. PHARMO (NL) (2.5 million Active Individuals)

The PHARMO Database Network, which is maintained by the PHARMO Institute for Drug Outcomes Research, is a population-based network of electronic health record databases that combines anonymous data from different primary and secondary health care settings in the Netherlands. These different data banks—including data from general practices, in- and outpatient pharmacies, clinical laboratories, hospitals, the cancer register, the pathology register, and the perinatal register—are linked on a patient level through validated algorithms. To ensure data privacy in the PHARMO Database Network, the collection, processing, linkage, and anonymisation of the data are performed by Stichting Informatievoorziening voor Zorg en Onderzoek, which is an independent, ISO/IEC 27001 certified foundation that acts as a trusted third party between the data sources and the PHARMO Institute. The longitudinal nature of the PHARMO Database Network enables the follow-up of more than 9 million individuals of a well-defined population in the Netherlands for an average of 12 years. Currently, the PHARMO Database Network covers over 6 million active individuals out of 17 million inhabitants of the Netherlands. Data collection period, catchment area, and overlap between data banks differ. Therefore, the final cohort size for any study will depend on the data banks that are required. All electronic patient records in the PHARMO Database Network include information on age, sex, socioeconomic status, and mortality. Other available information depends on the data banks. A detailed description of the different data banks is given in subsequent sections. The PHARMO Institute is always seeking new opportunities to link with additional databanks, currently, it is exploring linkage with the COVID-19 immunisation register that is collected by RIVM.

The General Practitioner databank comprises data from electronic patient records registered by GPs. The records include information on diagnoses and symptoms, laboratory test results, referrals to specialists, and health care product/drug prescriptions. The prescription records include information on the type of product, prescription date, strength, dosage regimen, quantity, and route of administration. Drug prescriptions are coded according to the WHO ATC coding system. Diagnoses and symptoms are coded according to the International Classification of Primary Care (ICPC) [www.nhg.org], which can be mapped to the International Classification of Diseases (ICD) codes but can also be entered as free text. General practitioner data cover a catchment area representing 3.2 million residents (~20% of the Dutch population).

The Outpatient Pharmacy Databank comprises GP- or specialist-prescribed health care products dispensed by the outpatient pharmacy. The dispensing records include information on the type of product, date, strength, dosage regimen, quantity, route of administration, prescriber speciality, and costs. Drug dispensing is coded according to the WHO ATC classification system. Outpatient pharmacy data cover a catchment area representing 4.2 million residents (~25% of the Dutch population). The PHARMO Database Network is listed under the European Network of Centres for Pharmacoepidemiology and Pharmacovigilance (ENCePP) resources database. PHARMO GP databank captures vaccinations supplied by the GP (influenza, zoster, COVID-19).

As of 08 May 2021, ~65,000 doses of Ad26.COV2.S vaccine have been administered in the Netherlands. Assuming PHARMO covers ~20% of the Dutch population, this should be 16,250 doses in PHARMO's catchment area. However, different healthcare providers administer the COVID-19 vaccines (i.e., GPs, the public health service and healthcare institutions) in the Netherlands. The vaccination data are recorded in a central register (if people have given permission beforehand), the COVID-19 vaccination Information and Monitoring System. PHARMO is currently exploring the possibilities to link with this register. Until then, the GP Database will be the basis for the vaccination data. The GP Database contains vaccinations administered by GPs and by the public health service, as GPs receive an automated notification when a patient has a positive corona test or has been vaccinated via the public health service (as long as people have given their consent).

It is difficult to estimate how many persons will be vaccinated with Ad26.COV2.S vaccine during the study period in the Netherlands. The Dutch government wants everyone from the age of 18 to have had at least one dose of COVID-19 vaccine by the beginning of July 2021. This vaccination schedule depends on many factors (e.g., approval and effectiveness, delivery and distribution of vaccines to injection sites, such as hospitals and GPs, new developments and advice from, for instance, the Health Council of the Netherlands (i.e., de Gezondheidsraad). Also, the choice of the type of vaccination depends on different factors, such as type of work (care workers), home living (yes or no), year of birth and existing comorbidities. PHARMO acknowledges that the data source they have access to includes data on vaccine delivery and registration and undertakes to cooperate in addressing the Study objectives by contributing to providing reports based on such data.

8.4.4. ARS Toscana Database (IT) (3.6 million Active Individuals)

Disclaimer: ARS Toscana's participation in the study is subject to the revision of the procedures for data access in the Tuscany Region. See section 8.2.1 regarding conditional participation of ARS Toscana.

The Italian National Healthcare System is organised at the regional level: the national government sets standards of assistance and tax-based funding for each region, which regional governments are responsible for providing to all their inhabitants. Tuscany is an Italian region, with approximately 3.6 million inhabitants. The Agenzia Regionale di Sanità della Toscana (ARS Toscana) is a research institute of the Tuscany region. The ARS Toscana database comprises all information collected by the Tuscany region to account for the health care delivered to its inhabitants. Moreover, ARS Toscana collects data from regional initiatives. All data banks in the ARS Toscana data source can be linked at the individual level through a pseudo-anonymous identifier. Two data banks collect dispensing of reimbursed medicines from, respectively, community pharmacies and hospital pharmacies. In the latter data bank, dispensing for outpatient and ambulatory use are complete, and dispensing for inpatient use are partial. Other data banks include hospital discharges, emergency care admissions, records of exemptions from co-payment, diagnostic tests and procedures, causes of death, the mental health services register, the birth register, the spontaneous abortion register, and the induced terminations register. A pathology register is available, mostly recorded in free text, but with morphology and topographic SNOMED codes. A COVID-19 registry including all positive cases with clinical follow-up is also available.

Mother-child linkage is possible through the birth register. Vaccination data are available for children since 2016 and for adults since 2019. All the data banks can be linked at the individual level through a pseudonymous identifier. Data banks are updated approximately every 2 months. Some of them are updated at the date of transmission (e.g., vaccines, COVID-19 registry, access to emergency room), while others (e.g., medicines dispensing and hospital discharge records) have a delay of approximately 4 months.

8.5. Study Size

The study will be conducted in a source population of approximately 18.1 million individuals, although children will not be vaccinated. It is assumed that up to 10% will be vaccinated with the Ad26.COV2.S vaccine.

8.5.1. Cohort

Subject to the feasibility assessment, a minimum target sample size of 100,000 individuals in the exposed cohort will be included in the study. [Table 2](#) shows the number of exposed subjects needed for various upper limits of the 95% CI of 2, 3, 5, and 10, assuming a ratio of 1:1 to unexposed or exposed and a power of 80% for different background incidence rates. For example, 80,000 individuals in the exposed cohort and 80,000 individuals in the unexposed cohort will allow the detection of an upper limit of the 95% CI of the relative risk equal to or greater than 3 with 80% statistical power for diseases with a background incidence rate of ≥ 100 per 100,000 person-years. We assume similar numbers of exposed comparators for those comparisons.

Table 2: Number of Exposed Subjects* needed to have an Upper Limit of the 95% CI of 2, 3, 5, and 10 Assuming a Ratio of 1:1 to Unexposed and a Power of 80% for Different Background Incidence Rates

Background IR per 100,000 PY	Upper limit of 95% CI for IRR			
	2	3	5	10
1	19,875,972	7,912,075	3,686,641	1,801,142
10	1,987,598	791,208	368,665	180,115
50	397,520	158,242	73,733	36,023
100	198,760	79,121	36,867	18,012

[Rothman 2018](#).

CI = confidence interval; IR = incidence rate; IRR = incidence rate ratio; PY = per year.

*Assuming each individual contributes a 60-day risk window.

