8.2. Setting and Study Population

8.2.1. Study Setting

For the implementation of the feasibility assessment, electronic health care databases in Southern and Western Europe that have shown interest and are members of the Vaccine Monitoring Collaboration for Europe (VAC4EU) will be used. The selected data sources and two-letter country codes are as follows:

- SIDIAP (Sistema d'Informació per el Desenvolupament de la Investigació en Atenció Primària) [Information System for Research in Primary Care] (ES)
- VID (La Fundació para el Fomento de la Investigación Sanitaria y Biomédica de la Comunitat Valenciana) [The Foundation for the Promotion of Health and Biomedical Research of Valencia Region] (ES).
- PHARMO DATABASE NETWORK (PHARMO Institute for Drug Outcomes Research) (NL)
- ARS Toscana (Agenzia Regionale di Sanità della Toscana) [a research institute of the Tuscany region of Italy] (IT)]. Since the approval of protocol version 2 by the EMA PRAC, a revision of the procedure for data access in the Tuscany Region has started. Hence, the study team at ARS Toscana has suspended its activities concerning the re-use of data until the revision of the procedures is complete. Until then ARS Toscana cannot contribute data to the study.

Further information on the data sources used in this study can be found in Section 8.4. When needed (based on specific safety concerns occurring in specific countries, or because of size) additional data sources may be added for dedicated evaluation studies, if they have adequate data on exposure, outcomes and covariates.

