8.5.2. Self-Controlled Risk Interval design

[Table 3](#) shows the statistical power that can be obtained for a range of relative risks and a range of sample sizes. For example, a sample size of 100 cases either in the risk or control window will allow the detection of a relative risk equal to or greater than 2 with 93% statistical power.

Table 3: Detectable Relative Risk and Statistical Power for SCRI Design

Relative Risk	Sample Size*	Power
1.5	20	14.2%
2	20	32.0%
2.5	20	49.5%
3	20	63.8%
1.5	50	29.2%
2	50	66.7%

Table 3: Detectable Relative Risk and Statistical Power for SCRI Design

Relative Risk	Sample Size*	Power
2.5	50	88.1%
3	50	96.3%
1.5	100	51.9%
2	100	92.6%
2.5	100	99.4%
3	100	100.0%
1.5	150	69.2%
2	150	98.7%
2.5	150	100.0%
3	150	100.0%
1.5	200	81.2%
2	200	99.8%
2.5	200	100.0%
3	200	100.0%

*Sample size = number of events in risk and control window.

Table 4 shows the number of vaccinated individuals assuming the same time in the control and risk window to obtain an 80% statistical power for a range of relative risks. For example, a sample size of 69 vaccinated individuals with an AE of interest will allow the detection of a relative risk equal to or greater than 2 with 80% statistical power.

Table 4: Detectable Relative Risk and Sample Size for 80% Statistical Power for SCRI Design

Relative Risk	Individuals with AE of Interest	Power
1.5	195	80.0%
2	69	80.5%
2.5	41	80.9%
3	29	80.4%

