8.7.1. Main Summary Measures

For the feasibility analysis the utilisation patterns of Ad26.COV2.S and other COVID-19 vaccines will be characterised and monitored over time. Description of demographics and clinical characteristics will be reported overall and for different groups of vaccine recipients.

The primary analysis will focus on calculating and comparing the incidence rates of each non-acute AESI between individuals exposed to Ad26.COV2.S and (1) unexposed individuals; (2) individuals exposed to another viral vector COVID-19 vaccine (i.e., Vaxzevria® [AZD1222] by Oxford/AstraZeneca); and 3) individuals exposed receiving a mRNA COVID-19 vaccine (cohort).

For acute events, the relative risk between risk window and control window will be estimated (using an SCRI design) among individuals exposed to Ad26.COV2.S. All analyses will be conducted within each data source and pooled across data sources using a random-effects model.

For the COVID-19 vaccines with a 2-dose schedule, AESI-specific risk windows after each dose of the comparator will be considered for the analyses. Further details on how to deal with different doses will be included in the SAP.

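### Table 2 sizes the cohort on a 60-day window that almost no cohort outcome uses; its worked example reads backwards, and the source population counts a suspended database

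*Protocol*

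**What the plan says.** Section 8.5.1 sets a minimum of 100,000 exposed individuals. Table 2 gives the number of exposed needed, at 1:1 matching and 80% power, for each "Upper limit of 95% CI for IRR" of 2, 3, 5 and 10, with the footnote "Assuming each individual contributes a 60-day risk window". The text reads one cell aloud: 80,000 per cohort "will allow the detection of an upper limit of the 95% CI of the relative risk equal to or greater than 3", at a background rate of 100 per 100,000 person-years or more.

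Sections 7 and 8.1.2 make the cohort the primary design for four non-acute outcomes, each with a window of days 1 to 365. For acute outcomes the cohort is a sensitivity analysis. Table 1 gives those outcomes windows of 0-2, 1-14, 1-28, 1-42 or 1-60 days, and only sensorineural hearing loss has 60.

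Section 8.5 opens: "The study will be conducted in a source population of approximately 18.1 million individuals". Section 8.2.1 says of one of the four databases: "Until then ARS Toscana cannot contribute data to the study".

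Section 8.5.2 gives self-controlled (SCRI) power by number of cases, for example "a sample size of 69 vaccinated individuals with an AE of interest will allow the detection of a relative risk" of 2 or more with 80% power. Section 8.7.1 adds: "All analyses will be conducted within each data source and pooled across data sources using a random-effects model".

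**The concern.** Section 8.5 is the protocol's only statement of what this safety study can exclude or detect. In Table 2 the number of people needed is inversely proportional to the days each contributes, so the assumed window drives every cell. A 60-day window describes none of the primary cohort outcomes and only one acute outcome. A reader using Table 2 to judge whether 100,000 exposed is enough gets the wrong answer in both directions: too gloomy for the 365-day outcomes, too hopeful for the short-window ones.

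Taken literally, the worked sentence promises an upper limit of 3 or more, the opposite of what a precision calculation offers. The source-population figure, and the number of vaccinated implied by the 10% uptake assumption, count a database that the same protocol says is unavailable.

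**Working it through.** **Inputs.** Two-sided 95% interval (z = 1.96), 80% probability (z = 0.8416), 1:1 ratio and 60 days per person, all from Section 8.5.1 and Table 2. Windows come from Table 1, and database sizes from the headings of Sections 8.4.1 to 8.4.4. The true IRR is taken as 1. The protocol does not state this, but Table 2 reproduces under it.

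**Reproducing Table 2.** With E events per arm, the log IRR has variance 2/E. Requiring the upper limit to fall below U with 80% probability when the IRR is 1 gives

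E = 2(1.96 + 0.8416)² / (ln U)²

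N = E / (rate × days/365)

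For U = 3, E = 15.698 / 1.2069 = 13.006. At 100 per 100,000 person-years and 60 days, N = 13.006 / (0.001 × 60/365) = 79,121, the printed value. All 16 cells reproduce to within one person, so the arithmetic is right for the assumption made.

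**The same formula at the actual windows** (rate 100 per 100,000 person-years). The last column inverts it: U = exp(2.8016 × √(2/E)), with E = 100,000 × 0.001 × days/365.

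| Days per person | Exposed needed for U = 3 | Relative to 79,121 | U met with 80% probability at 100,000 exposed |
|---|---|---|---|
| 365 | 13,006 | 0.16 | 1.49 |
| 60 | 79,121 | 1.0 | 2.66 |
| 42 | 113,030 | 1.4 | 3.2 |
| 28 | 169,544 | 2.1 | 4.2 |
| 14 | 339,089 | 4.3 | 7.6 |
| 3 (days 0-2) | 1,582,415 | 20 | about 79 (0.8 expected events; the approximation is not usable) |

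The 365-day row assumes a full year of follow-up in both arms. Sections 8.2.3 and 8.3.1 censor the unexposed at any COVID-19 vaccine, and the exposed at a different COVID-19 vaccine or a second Ad26.COV2.S dose. The factor 365/60 = 6.1 is therefore an upper bound. As an illustration, a mean of 180 days in both arms gives 13.006 / (0.001 × 180/365) = 26,374, which is 3.0 times fewer than printed. The protocol gives no expected mean follow-up.

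The window factors are the same at every background rate, but a conservative table does not mean ample precision for rare outcomes. At 10 per 100,000 person-years, 100,000 exposed with a full 365 days yields 10 events per arm and an upper limit of 3.5.

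**The worked sentence.** At 80,000 per arm, 60 days and this rate, E = 13.15. The probability that the upper limit is below 3 is Φ(ln 3 / √(2/13.15) − 1.96) = 0.80. The 80% belongs to the event that the limit is below 3, not at or above it.

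**Source population.** 7 + 5 + 2.5 + 3.6 = 18.1 million. Without ARS Toscana it is 18.1 − 3.6 = 14.5 million, 20% fewer. At 10% uptake this gives up to 1.45 million vaccinated instead of 1.81 million.

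**Tables 3 and 4.** The signed-root likelihood-ratio formula for equal windows reproduces the cells checked to within 0.3 points, for example 92.6% at RR 2 with 100 cases and 80.5% at RR 2 with 69. It uses only the RR and one undivided case count. No window length, population figure or between-database variance enters.

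**The case against.** The strongest reply is that little turns on this. For the primary cohort outcomes the 60-day assumption errs on the safe side. The optimistic side touches only sensitivity analyses, for which Section 8.5.1 makes no explicit 80% claim. The target is subject to the feasibility assessment, and every requirement tabulated above down to 14 days is below 1.45 million. The Table 2 title makes the intended meaning of the worked sentence recoverable. The status of ARS Toscana is disclosed in several other sections.

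Most of that stands, and it limits the point to how study size is reported. It does not make 60 days the right basis for the table, nor the sentence correct as written.

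Three stronger readings are tempting and unsupported:

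- A reader might infer that the 60-day window undermines power for the primary acute analyses. It does not: Tables 3 and 4 rest on case counts and equal risk and control time.
- A reader might infer that losing ARS Toscana invalidates the stated precision or power. No cell of Tables 2 to 4 is computed from 18.1 million, and the protocol does not derive the 100,000 target from it.
- A reader might infer that Tables 3 and 4 overstate power by a known amount because of random-effects pooling. The protocol names no estimator, heterogeneity or split of cases between databases, and Section 8.7 leaves pooling detail to the SAP. The direction is clear; the size cannot be obtained from the document.

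**Conclusion.** The point holds as a fault in the study-size statement. Table 2 is correct for 60 days but does not describe the planned cohort analyses. It is conservative for the 365-day primary outcomes, by up to 6.1 times and by less once censoring is counted. It is optimistic for the acute cohort analyses other than hearing loss, by 1.4 to 4.3 times for windows of 42 to 14 days and 20 times for the three-day anaphylaxis window. The worked sentence states the reverse of what the table delivers. The population of 18.1 million should be 14.5 million while ARS Toscana is suspended.

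These figures rest on the protocol's own inputs, a true IRR of 1 and the normal approximation on the log scale, which is weak where few events are expected. For the SCRI, the most that can be said is that Tables 3 and 4 carry no heterogeneity term, so power under the planned pooling will be lower by an amount that depends on the estimator and the heterogeneity. No planned analysis is shown to be invalid.

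**What to change.** - Restate Table 2 by actual risk window (365, 60, 42, 28, 14 and 3 days). Let the 365-day row allow for censoring at COVID-19 vaccination, or show it over a range of mean follow-up. Add the upper limits attainable at the 100,000 minimum.
- Reword the example: about 80,000 per cohort, each followed for 60 days, gives an 80% probability that the upper 95% limit lies below 3 if the true IRR is 1 and the background rate is 100 per 100,000 person-years. State the IRR of 1 as an assumption of the table.
- Give the source population as 14.5 million, with up to 1.45 million vaccinated at 10%, and 18.1 million only if ARS Toscana returns. Make the same change in the abstract.
- Add a note to Tables 3 and 4 that they apply to a single undivided case count without between-database heterogeneity, and that power after random-effects pooling will be lower.

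The cost is a rewrite of Section 8.5 and the matching abstract lines. No data, design or analysis changes. Some stated figures become less favourable for the short-window cohort analyses, and those for the primary outcomes become more favourable.
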